Study Background and Rationale: Among patients receiving opioids for noncancer pain, recent research in North America showed a strong association between doses and opioid-related mortality, especially at dosages exceeding thresholds recommended in recent guidelines. However, the focus on over-dosage may underestimate overall opioid-related mortality and data on death associated with opioid use in a population-based cohort of chronic noncancer pain patients in Europe is scarce. Especially comparative studies studying the safety of long-term opioid therapy in a real-world setting relative to non-opioid medication for chronic noncancer pain are needed in a European context.

Research Question and Objective(s): The primary objective is to investigate the association between mortality among patients with chronic noncancer pain with long-term opioid-therapy compared to non-opioid pain medication. The secondary objectives are to determine the risk of addiction/abuse and hospital admissions among opioid users with chronic non-cancer pain compared to patients with non-opioid pain medication.

Study Design/Type: This is a cross-sectional observational cohort study between 2012 and 2017 of patients with chronic noncancer pain.

Study Population and Data Resource: The data will be retrieved from an anonymized German health claims database including 4,00,000 persons insured by 69 German statutory health insurances. The data set includes 5.0% of the population covered by statutory health insurances

from January 1, 2012, to December 31, 2017. Only anonymized and aggregated data (no directly or indirectly identifying data) will be extracted.

Summary of Patient Eligibility Criteria: From the data extraction, the cohort will be analysed according to the following criteria:

Inclusion criteria: At least one diagnosis of pain R51 (headache), R52* (pain, not elsewhere classified), M00 – M99 (Diseases of the musculoskeletal system and connective tissue), G43* (migraine), G44* (other headache syndromes), G50.0 (trigeminal neuralgia), G50.1 (atypical facial pain), F45.4* (persistent somatoform pain disorder), G62* (polyneuropathies), E10.4*-E14.4 plus G63.3 (diabetes mellitus with neurological complications) in at least 3 quarters between 01.01.2012 and their first opioid claim AND opioid medication (Cohort A) OR non-opioid medication (Cohort B) between 01.01.2012 and first pain medication claim.

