9.2 Setting and Study Population

The database contains data on around 4 million insured people from 69 German statutory health insurances (SHI). German SHI system comprises of approximately 120 independent health insurance companies. Funds paid by these SHI to any provider of health care (e.g. hospitals, physicians, pharmacies, psychotherapists and physiotherapists) represent almost the complete picture of the total health care costs of individual patients. All health insurance data can be linked to patients' demographics including age and gender. Health care data in the database include:

- Patient demographics:
 - age
 - gender
 - date of death

- region of residence
- insurance status
- date of insurance start and end
- Hospital care:
 - main diagnosis (ICD-10-GM codes) and additional diagnoses
 - procedures and surgeries
 - date of hospital admission
 - reason for admission (e.g. accident, emergency, normal)
 - date of end of hospital stay
 - reason of end of hospital stay (e.g. regular discharge from hospital, death)
 - DRG-Code
 - costs
- Outpatient care:
 - diagnoses (ICD-10-GM codes)
 - quarter in which the diagnosis was documented
 - procedures performed (EBM codes, e.g. laboratory tests, radiology, echocardiography) and date of procedure
 - type of specialist that documented the diagnosis and performed the procedure (e.g. cardiologist, general practitioner)
 - costs
- Pharmaceutical claims:

- drug dispensed (PZN code, which identifies medications at the package level) – this is mapped to ATC codes and DDDs
- quantity dispensed
- day of prescription
- day of dispensing
- type of specialist prescribing the medication (e.g. general practitioner)
- costs of drugs dispensed from the perspective of the statutory health insurance (without individual rebates between insurance and pharmaceutical companies)
- Physical therapy and technical aids:
 - type of therapy (e.g. massage, occupational therapy, walker, wheel chair)
 - quantity prescribed
 - type of care provider
 - start and end date
 - costs
- Sick leave:
 - diagnoses that cause sick leave
 - duration of sick leave
 - start date of sick leave
 - end date of sick leave

- type of specialist that filled out the sick leave form (e.g. general practitioner)
- costs of sick leave

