9.2.2 Patient Eligibility

9.2.2.1 Inclusion Criteria

For the purposes of this study, the requested extraction of the database consists of population of patients with chronic non-cancer pain corresponding to the following criteria. Inclusion and exclusion criteria are also provided in Figure 2.

Figure 2: Inclusion and exclusion criteria

Cohort A

- Patients are included in the long-term opioid group if they started an opioid-therapy between 2013 and 2017 and received consecutive prescriptions for opioid medications over a minimum of 3 quarters, over a 60-month period between January 1, 2013, and December 31, 2017. The treatment will be assessed using the ATC codes of opioid treatment N02AA01, N02AA05, N02AB03, N02AE01, N02AX02, N02AX01, N02AX06 (see also Table 9-1) reported in reimbursed medicines to patients.

- Patients are only included if they have been diagnosed in at least three quarters in the study period with one of the following diagnoses: R51, R52*, M00*-M99*, G43*-G44*, G50.0 or G50.1, F45.4*, G62*, or E10.4*-E14.4 plus G63.3. At least one diagnoses must be between 1 January 2012 and index treatment and main and secondary hospital diagnoses (*i.e. Haupt- und Nebendiagnosen*) will be used to include the patients.

Cohort B

- Patients with non-opioid pain medication are included, if they received a medication therapy with anticonvulsants (gabapentin, pregabalin, carbamazepine), antidepressants or non-opioid analgesics (NSAIDs, Metamizole) over a minimum of 3 quarters, over a 60-month period between January 1, 2013, and December 31, 2017. The non-opioid treatment will be assessed using the ATC codes (N03AX12, N03AX16, N03AF01, see also Table 9-1) of treatment reported in reimbursed medicines to patients.
- Patients are only included if they have been diagnosed in at least three quarters in 2012 with one of the following diagnoses: R51, R52*, M00*-M99*, G43*-G44*, G50.0 or G50.1, F45.4*, G62*, or E10.4*-E14.4 plus G63.3. At least one diagnoses must be between 1 January 2012 and index treatment and main and secondary hospital diagnoses (*i.e. Haupt- und Nebendiagnosen*) will be used to include the patients.

All diagnoses that lead to patient inclusion when coded between 01.01.2012 and index treatment and in at least three quarters within the study period are provided in Table 9-2 below.

Table 9-1: List of ATC codes of study opioid and non-opioids

Name	ATC Code
Study opioids	
Morphine	N02AA01
Oxycodone	N02AA05
Fentanyl	N02AB03

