9.4.2.2 Secondary endpoints

Secondary endpoints are following:

- **Hospitalization due to any course.** Hospitalization will be assessed via the number of hospitalisations (calculated by counting the number of discharge dates (KH_Fall. Entlassungsdatum) in the year of interest, hospitalization rate, and length of stay in the hospital (KH_Fall. Verweildauer). The rate of hospitalization will be estimated as the number of patients with at least one hospitalization during the follow-up period divided by person-time of follow-up, censoring at time of death, last known record for the patient in the database, or 31st December 2017 (end of latest data cut), whichever is earlier.
- **Intensive care unit (ICU-stay)** stay is defined as patient's stay based on specialty of department in hospital (KH_OPS.Fachabteilung = 3600).
- **Hospitalization with to misuse or addiction.** The hospitalization with misuse or addiction will be analysed, if principal (main) diagnosis at discharge date between January 1st 2013 and December 31st 2017 contains at least one ICD-10 diagnosis of misuse/addiction: F10* or F11* or F13* or F19* or T40* (see also Appendix B in **Fehler! Verweisquelle konnte nicht gefunden werden.**).
- **Hospital admission diagnoses.** We report the hospital admission diagnoses based on ICD-10 codes between January 1st 2013 and December 31st 2017.
- **Coding of procedures in hospitals** that indicate number of patients that were hospitalized with severe diseases such as cardiovascular

diseases will be assessed via OPS-Codes provided in Appendix B as an excelsheet.

- **Coding of a misuse or addiction diagnosis in the outpatient sector** will be assessed via number of codings of misuse/addiction (ICD Codes = F10* or F11* or F13* or F19* or T40*) in outpatient sector by general practitioner or a specialist (e.g. psychiatrist), as ensured diagnosis (Diagnosesicherheit='G'). Additionally, the number of patients with a least one coding of ICD 10 codes of an ensured misuse/addiction in outpatient sector by general practitioner or a specialist (e.g. psychiatrist) will be assessed.
- **Sick leave** will be assessed as an absolute number and relative frequencies of patients with an attest of inability to work (patients with attest of inability to work as a percentage of all patients) in 2013-2017 and number of days being off work.
- **Hospital deaths** will be assessed via reason of discharge = death (Entlassgrund = Tod)

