9.5 Validity and Reliability

The external validity of the used data set is checked against the national reference data from official resources: Information System of the Federal Health Monitoring for the total German population and from the German Drug Prescription Report for the German population insured within the SHI system (Anderson et al., 2016). The reliability of each outcome variable (i.e., diagnoses) will be warranted due to the use of only “ensured”

(instead of suspected diagnosis) outpatient diagnoses or inpatients diagnoses.

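### Section 9.2.2.1 names only hospital diagnoses as the source for inclusion and gives the two cohorts different three-quarter windows, so the compared populations are not fixed

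*Protocol*

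**What the plan says.** **Source.** Each cohort bullet in section 9.2.2.1 ends by stating that "main and secondary hospital diagnoses (*i.e. Haupt- und Nebendiagnosen*) will be used to include the patients". The three-quarter sentence that precedes it names no care setting.

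**Window.** Four statements are made:

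- Cohort A bullet: patients must be "diagnosed in at least three quarters in the study period with one of the following diagnoses".
- Cohort B bullet: patients must be "diagnosed in at least three quarters in 2012 with one of the following diagnoses".
- The sentence introducing Table 9-2, which covers both cohorts: at least one code before index treatment, and three quarters anywhere in the study period.
- Synopsis, eligibility summary: the diagnosis must be present "in at least 3 quarters between 01.01.2012 and their first opioid claim".

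Both bullets also require at least one diagnosis between 1 January 2012 and index treatment.

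**The concern.** These criteria define who is compared. Section 9.2.2.1 presents them as the specification of the database extraction, and section 9.6.1 says that the insurers' data authority will obtain the data on the basis of this protocol. Whoever programs the extraction has to choose a diagnosis source and a window, and the text does not settle either.

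Two things are at stake. If hospital codes alone are used, a patient needs hospital-coded pain in three separate quarters. That selects people who are admitted repeatedly, and it bears directly on the primary endpoint (death from any cause) and on the hospitalisation endpoints. It would also fit poorly with the stated aim of describing chronic noncancer pain patients under real-world care. Separately, if the two cohort bullets are followed as written, the cohorts differ in how chronicity was established before any matching takes place. Propensity matching on the listed covariates does not undo a difference in the entry rule.

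**Working it through.** No sample size, power figure or event count depends on this rule, so the check compares the relevant text.

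**1. Diagnosis source: every place that names one**

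- Synopsis: gives the diagnosis rule with no source and no hospital restriction.
- Section 9.2: the database holds outpatient diagnoses, recorded by "quarter in which the diagnosis was documented". Hospital stays carry admission and end dates.
- Section 9.2.2.1: hospital main and secondary diagnoses, in both bullets. Outpatient diagnoses are not mentioned.
- Section 9.2.2.2, cancer exclusion: hospital main and secondary diagnoses are taken into account. Again, no outpatient source is named.
- Section 9.4.2.2: for outpatient misuse or addiction, the source is explicit: codings "in outpatient sector by general practitioner or a specialist (e.g. psychiatrist), as ensured diagnosis", with certainty flag G.
- Section 9.5: refers to ensured "outpatient diagnoses or inpatients diagnoses", but the sentence begins "The reliability of each outcome variable (i.e., diagnoses) will be warranted due to the use of only". It covers outcomes, not inclusion.

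So hospital coding is the only source named for inclusion. Where outpatient codes are meant elsewhere, the protocol says so. On the other side, a rule that counts quarters matches the way outpatient diagnoses are dated, and the synopsis carries no restriction. The likely intention is that both sources count, but nothing states it.

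**2. Window: quarters available**

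- Study period, 1 January 2012 to 31 December 2017: 6 years × 4 = 24 quarters. Cohort A needs 3 of 24.
- 2012 only: 1 year × 4 = 4 quarters. Cohort B needs 3 of 4.
- Before index: index treatment falls between 1 January 2013 and 31 December 2017, so the window holds at least 4 full quarters. At the latest index date it holds 23 full quarters plus part of the 24th.

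The Table 9-2 sentence contradicts the Cohort B bullet. The synopsis contradicts both the Cohort A bullet and the Table 9-2 sentence. Its end point, the first opioid claim, also does not exist for a Cohort B patient who never receives an opioid.

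**3. Survival after index**

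Under the Cohort A bullet, one diagnosis must precede index treatment, so up to two of the three quarters may come afterwards. Follow-up starts at index. A patient who starts opioids with one coded quarter and dies before two more are coded never enters Cohort A. Under the Cohort B bullet, all three quarters lie in 2012, before any possible index date, so the diagnosis rule imposes no such condition. Taken alone, this would lower observed mortality in Cohort A relative to Cohort B. How far depends on how many Cohort A patients rely on post-index codes, which the documents do not give.

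**The case against.** The strongest counter-argument is that the text never says *only*. The hospital clause follows the sentence on the pre-index diagnosis and can be read as meaning that secondary as well as main hospital codes count, in addition to outpatient ones. Section 9.4.2.2 restricts misuse hospitalisations to the principal diagnosis, so main versus secondary is a distinction the authors draw on purpose. The parallel wording in the cancer exclusion also reads as additive. This stands. A reader might infer that the protocol limits the study to hospital-coded patients; the documents do not support that as the only reading.

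A reader might also infer that Cohort B would be far smaller or far sicker than Cohort A. The documents give no share of pain patients coded in hospital and none coded in outpatient care, so no percentage can be defended. Any gap in the number qualifying that comes from 3 of 4 versus 3 of 24 quarters is due to the window, not to the diagnosis source.

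Finally, Figure 2, which repeats the criteria, is not in the available text, and an analysis plan might specify sources. That could resolve the ambiguity over source. It would not remove the conflict between the cohort bullets, the Table 9-2 sentence and the synopsis, all of which stand in the protocol.

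**Conclusion.** The point holds as an incomplete and internally inconsistent inclusion rule. The source is incomplete: hospital diagnoses are named, outpatient diagnoses are not, and a literal extraction would yield a repeatedly hospitalised cohort. That consequence is conditional on the literal reading, and the surrounding text favours the broader one. The window is contradictory on any reading: 24 quarters for A, 4 for B, 24 for both, or the quarters before the first opioid claim. Following the bullets would select the compared cohorts by different rules and add a survival condition to Cohort A only.

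The effect on cohort size, mortality rates or the hazard ratio cannot be quantified from the documents. The direction given for the survival condition assumes that the two bullets are applied as written and that some Cohort A patients qualify through post-index codes. It does not settle the net bias, because 3 of 4 quarters in 2012 may also select a different severity of pain.

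**What to change.** In both cohort bullets, state that a pain diagnosis counts if it is an ensured outpatient diagnosis (flag G) or a hospital main or secondary diagnosis. Make the source in the cancer exclusion of section 9.2.2.2 equally explicit.

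Reconcile the two bullets, the Table 9-2 sentence and the synopsis to one identical window. A window from 1 January 2012 to index treatment is preferable: it follows the synopsis, and the diagnosis criterion then no longer depends on surviving after index. Replace the synopsis's end point with index treatment so that it applies to both cohorts.

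The cost is about one sentence per cohort and a synopsis edit if done before extraction; afterwards, extraction, matching and analysis would have to be repeated. A pre-index window drops some patients whose pain codes accrue later. Its length also varies with index date, from 4 quarters upwards; index year is already in the propensity model and index quarter in the Cox model. The separate requirement of treatment in three quarters still depends on survival in both cohorts, and this change does not address it.

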9.2.1 Study Period

Due to data protection regulations in Germany, only an extract of maximum 6 years of data coverage could be available for the research purposes: 1st January 2012 to 31st December 2017.

The **baseline period** is defined as the period prior to the date of first diagnosis of diagnoses or first opioid or non-opioid treatment initiation as described in inclusion criteria (Chapter 9.2.2.1). The baseline assessment period endures between January 01, 2012 and first study medication prescription.

Index treatment is defined as the date of first opioid or non-opioid treatment prescription between 1st January 2013 and 31st December 2017.

Exposure time is defined as time between index treatment and December 31, 2017. Considering data availability of a maximum of 6 years and prescription in a required time period of 60 months, exposure time endures maximum five years. Thus, patients can be censored at death (death date in the linked records), last known record for the patient in the German health claims database, switching of treatment groups (from opioid group to non-opioid group or vice versa), 12 months without opioid/non-opioid treatment or 31st December 2017 (end of latest data cut), whichever comes first.

[figure not shown]
The **outcomes** will be assessed between index treatment and 31.12.2017.

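### The three-quarter pain-diagnosis rule has incompatible windows; as the cohort bullets stand, Cohort B must qualify within 2012 while Cohort A may qualify on diagnoses made after index

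*Protocol*

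**What the plan says.** The protocol states the diagnosis window in four places.

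- Section 9.2.2.1, Cohort A: patients must be "diagnosed in at least three quarters in the study period with one of the following diagnoses".
- Section 9.2.2.1, Cohort B: "Patients are only included if they have been diagnosed in at least three quarters in 2012 with one of the following diagnoses".
- Section 9.2.2.1, sentence introducing Table 9-2 (a table headed for both cohorts): diagnoses lead to inclusion "when coded between 01.01.2012 and index treatment and in at least three quarters within the study period".
- Opening summary, patient eligibility criteria: a listed diagnosis "in at least 3 quarters between 01.01.2012 and their first opioid claim", given as one window for both cohorts.

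Both cohort bullets add: "At least one diagnoses must be between 1 January 2012 and index treatment".

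Section 9.2.1 fixes the calendar. On the data it says "only an extract of maximum 6 years of data coverage could be available for the research purposes: 1st January 2012 to 31st December 2017". On index it says "Index treatment is defined as the date of first opioid or non-opioid treatment prescription between 1st January 2013 and 31st December 2017". All of 2012 therefore precedes every index date. Outcomes are counted from index, and the primary endpoint (Section 9.4.2.1) is death from any cause.

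**The concern.** The primary objective compares mortality between opioid and non-opioid patients with the same kind of chronic pain. If the diagnosis rule differs by cohort, two things follow.

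1. **Pain history.** A patient whose pain is first coded in 2014 can enter Cohort A but never Cohort B. A Cohort B patient with index in 2016 must have had pain coded in three of the four quarters of 2012, a year in which Section 9.2.2.2 allows no study pain medication. Section 9.3.1 names region, comorbidities, comedication, year of index, dosage, procedures, age and gender as matching variables. Section 9.3.2 adds the comorbidity index, treatment duration, quarter of index and the propensity score. None of these names the onset or duration of pain or the number of diagnosis quarters.

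2. **Guaranteed survival.** A Cohort A patient with fewer than three diagnosis quarters at index must live, and stay insured, long enough to collect the rest, yet follow-up counts from index. A Cohort B patient has met the diagnosis rule before follow-up starts.

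Section 9.10.1.3 calls selection bias less likely in claims data and does not mention either point.

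**Working it through.** The protocol has no sample size, event count or power figure that depends on this rule, so there is nothing of its own to reproduce. The check compares the windows and then sizes the effect under stated assumptions.

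**Step 1. The four rules side by side**

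| Source | Cohort A window | Cohort B window | Can post-index quarters count? |
|---|---|---|---|
| Cohort bullets | 2012–2017 (24 quarters) | 2012 (4 quarters) | A yes, up to 2 of 3; B no |
| Sentence before Table 9-2 | 2012–2017 | 2012–2017 | Both yes |
| Opening summary | Up to first opioid claim | Up to first opioid claim | A no; B unclear |

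In Cohort B a first opioid claim either never occurs or comes after index as a switch, so the summary's cut-off does not define a baseline there.

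**Step 2. How much stricter the Cohort B bullet is (illustration)**

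Assume pain is coded in each quarter independently with probability p. The documents give no p, so a range is shown. Let k be the number of quarters before index, from 4 (index in Q1/2013) to 23 (Q4/2017, the calendar limit).

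- Cohort B: P(at least 3 of 4) = 4p³(1−p) + p⁴. At p = 0.2 this is 0.0256 + 0.0016 = 0.027.
- Cohort A: P(at least 3 of 24) − (1−p)^k × P(at least 3 of 24−k). At p = 0.2 and k = 4 this is 0.8855 − 0.4096 × 0.7939 = 0.560.

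| p | Cohort B | Cohort A, k = 4 to 23 |
|---|---|---|
| 0.1 | 0.004 | 0.22 to 0.44 |
| 0.2 | 0.03 | 0.56 to 0.89 |
| 0.3 | 0.08 | 0.76 to 0.99 |
| 0.5 | 0.31 | 0.94 to 1.00 |
| 0.8 | 0.82 | about 1.00 |

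The Cohort B bullet is stricter at every p tried, most of all for patients whose pain is coded infrequently.

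**Step 3. The survival component taken alone**

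Assumptions: the same true mortality λ = 0.015 per year in both cohorts (the middle of the 100 to 200 per 10,000 person-years in Section 9.3.1); censoring uniform between 0.4 and 4.0 years (mean follow-up about 2.2 years); both cohorts alive and observed at 0.25 years because of the prescription rule; and a share s of Cohort A that must stay alive and observed for a further exponential wait with mean w. The documents give neither s nor w.

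With constant mortality, the observed rate is λ × (person-years after the guaranteed span) / (all person-years). For Cohort B this is about 0.015 × (1 − 0.25/2.16) = 0.0133 per year. The A/B rate ratios, by numerical integration, are:

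| Share s | w = 3 months | w = 6 months | w = 12 months |
|---|---|---|---|
| 10% | 0.99 | 0.98 | 0.97 |
| 30% | 0.97 | 0.94 | 0.92 |
| 50% | 0.94 | 0.90 | 0.86 |

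Simulation of the four cells with s of 30% or 50% and w of 6 or 12 months gave 0.943, 0.920, 0.905 and 0.861, in agreement.

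**Step 4. Does the net bias have a sign?**

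In Section 9.2.2.1 the three prescription quarters must be consecutive in Cohort A, but that word is absent for Cohort B. Cohort B may therefore take longer to complete its prescription rule, which guarantees survival there. Start from the cell s = 30%, w = 6 months (0.943). If 30% of Cohort B also waits an extra mean 6 months, the two effects cancel: 0.943/0.943 = 1.00. If 50% does, the ratio is 0.943/0.905 = 1.04. The sign depends on inputs that the protocol does not give.

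**The case against.** The strongest reply is that the 2012 limit is a slip. The Cohort B bullet goes on to require at least one diagnosis before index. That would be redundant if all three quarters had to lie in 2012, since index cannot precede 2013. The sentence before Table 9-2 and the opening summary each give a common window. Figure 2, said to show the criteria too, is not in the text available. This stands as a reason not to call the asymmetry a deliberate choice. It does not remove the problem: the two common windows disagree with each other, and a programmer cannot tell which text governs. If the common study-period rule was meant, the asymmetry goes, but eligibility in both cohorts still depends on diagnoses made after index.

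A reader might also infer three stronger things that the documents do not support.

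- *That the plan will show a protective opioid effect of 6 to 14%.* Those figures correspond to shares of 30 to 50% and waits of 6 to 12 months, all assumed. One diagnosis must precede index, so at most two quarters are outstanding. If pain is coded in the same quarters as the consecutive opioid prescriptions, the extra wait is near zero. Step 4 shows that the net direction is not fixed either.
- *That matching cannot repair the imbalance.* Section 9.3.1 refers to other comorbidities and to Appendix A, which is not shown. One can say only that no visible covariate names pain history.
- *That Cohort B is previously untreated.* Section 9.2.2.2 excludes prior pain-medication prescriptions in 2012, in both cohorts. It does not exclude physical therapy, for example.

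**Conclusion.** The point holds as an internal contradiction in the eligibility text, with consequences for the primary comparison if the cohort bullets are programmed as written. In that case pain onset after 2012 can enter only Cohort A, and only Cohort A can complete the diagnosis rule after index. The resulting difference in pain history cannot be sized from the document. The additional guaranteed survival lowers Cohort A mortality when taken alone, with a rate ratio from about 0.99 (10% waiting an extra 3 months) to about 0.86 (50% waiting an extra 12 months). These are crude rates under equal constant mortality of 150 per 10,000 person-years, not matched Cox estimates, and they rest on assumed shares and waits. The net bias of the protocol as a whole cannot be signed. Because the rule decides who is compared on mortality, it should be settled before the cohorts are extracted.

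**What to change.** Use one rule for both cohorts, ending at index: at least three quarters with a Table 9-2 diagnosis between 1 January 2012 and index treatment. In Section 9.2.2.1, delete the study-period wording for Cohort A and the 2012 wording for Cohort B, and align the sentence before Table 9-2. In the opening summary, replace the first opioid claim with index treatment. Check Figure 2 against the result.

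The cost is wording and extraction code. Cohort A loses patients whose third diagnosis quarter comes only after index; relative to its present bullet, Cohort B gains patients with pain onset after 2012. One weakness remains: the look-back still runs from 4 to 23 quarters depending on index date. At p = 0.2 in the Step 2 illustration, the chance of qualifying is 0.03 with 4 pre-index quarters, 0.55 with 14 and 0.87 with 23, but it is now the same in both cohorts for a given p and index date. The planned covariates for year and quarter of index treatment partly address this. The change does not touch the post-index survival built into the prescription rule, which is a separate matter.
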